	A subset of subjects in Cohort 7 and 8 (Cohorts 7A, 8A and 8B) will have a second sensor type placed on the pectoralis or sternum. This sensor (the 2-Part Brilliance Sensor) is being tested to evaluate a removable adhesive ring that would allow future re-use of the sensor portion.
Treatment:	Eligible subjects will receive a single dose of MB-102 followed by a single dose of iohexol (Groups 1 and 2). Group 3, Cohorts 5, 6, SOG, SeVG-1, SeVG-2 and Cohort 8 will only receive a single dose of MB-102 and will not receive iohexol. A subset of subjects in Group 3, Cohort 7 will receive 2 doses of MB-102. Blood draws will be taken at pre-defined timepoints and the Optical Renal Function Monitor (ORFM) fluorescent measurements will be collected over an 8 - 12 hour period or up to 24-48 hours in certain cohorts.
	Group 1, Cohort 1 subjects may receive a range of doses of MB-102. Assessments of coefficient of variation will determine dose optimization. Remaining Group 1 subjects and Group 2 subjects will receive the optimized dose.
	Group 3 subjects (cohorts 5, 6, SOG and over half the subjects in the SeVG cohort will receive a single dose of 4 µmol/kg. A subset of the SeVG cohort (approximately 20 subjects who weigh greater than 110 lbs (50 kg) will receive a fixed dose of 7 mL (130 mg) MB-102.
	Cohorts 7 and 8 (regardless of weight) will all receive a fixed dose of 130 mg (7 mL).
	A subset of Group 3 subjects in Cohort 7 will receive 2 doses of MB-102 (fixed dose of 7 mL (130 mg). The 2 nd dose will be administered 12 hours after the first dose. For Cohort 7B, subjects will receive their 2 nd dose 24 hours after the first dose.
	Sensor placement in all subjects from Groups 1 and 2 will be in two different locations. All Group 1 and 2 subjects will have a single sensor placed on the sternum. A second location will be assigned to determine additional sites for fluorescent measurements. Group 3 subjects may have 2-3 different sensors located on different parts of the body. At least one sensor will be on the sternum or pectoralis major.  • Group 1 subjects will have fluorescent measurements performed by the
	
 
Prototype QuantumLeap device.
 
Group 2 subjects will have fluorescent measurements performed by the Prototype Radiance device.
 

	Group 3 subjects will have fluorescent measurements performed by the Prototype Brilliance device.

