	• Any other serious or uncontrolled medical disorder, active infection, physical exam finding, laboratory finding, or psychiatric condition that in the opinion of the investigator would limit the subjects' ability to complete study requirements or may put the subject at increased risk or compromise interpretability of study results. Note: a history of gallstones or kidney stones are not excluded so long as the condition is not acute within 30 days of dosing.
	Additional Exclusion: Group 2 Cohort, 4 and Group 3 Cohorts 6, SeVG-2, and 8
	
 
Recent (within 3 months) significant medical condition or surgical procedure including myocardial infarction, thoracic laparoscopic procedures, or other significant medical inventions
 
Received >20 mg/day of prednisone or an equivalent dose of glucocorticoid for more than 7 days in the last 90 days prior to dosing day
 

	for an acute or chronic disorder
	Currently receiving dialysis
	Currently anuric
Primary Endpoint:	
 
Determine plasma pharmacokinetics of MB-102 compared to the pharmacokinetics of iohexol in subjects with normal and impaired renal function and a range of skin color types (Groups 1 and 2)
 
To show that the MB-102 transdermal fluorescence measured GFR using the ORFM Brilliance device matches the measured MB-102 plasma GFR (Group
 

Casandawy	3) SATE 14 1 SATE 102
Secondary Endpoints:	• Evaluate the safety and tolerance of MB-102
Endpoints:	• Evaluate the safety of the ORFM devices for the noninvasive transdermal fluorescent detection of MB-102
	• Evaluate the effectiveness of the ORFM devices (QuantumLeap, Radiance and Brilliance) through the comparison of fluorescent measurements versus MB-102 across the three groups of subjects
	Determine the optimum dose of MB-102 for noninvasive measurement
Primary Safety Endpoint:	Adverse events (AEs and serious AEs [SAEs], UADEs)
Statistical Methods and Sample Size	As this is a Pilot Study, no formal calculation of sample size was conducted.
Calculations	Safety will be evaluated as the incidence of AEs and SAEs/UADEs. These will be summarized by cohort and overall.
Time Schedule:	Planned Start of Study: April 2016
i inic schedule.	
	Planned End of Study: Sep 2021

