In the Pilot 2 Groups 1 and 2, the first blood draw was taken at 5 minutes post administration of MB-102, and the last at 12 hours post administration. The transdermal fluorescence was measured at the sternum and one other location for each subject using the prototype device QuantumLeap and Radiance. For all 120 subjects over the wide range of GFR values, the following were observed:

- A two compartment plasma pharmacokinetic profile
- A high correlation between the MB-102 and iohexol plasma derived GFR values
- A high correlation between the MB-102 plasma and transdermal fluorescence pharmacokinetics

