### 4 Study Objectives

The objectives of this pilot study are:

- To evaluate the safety and tolerability of single dose and multiple doses of MB-102 in subjects with normal and impaired kidney function
- To determine plasma pharmacokinetics of MB-102 compared to the pharmacokinetics of iohexol in subjects with normal and impaired renal function (Groups 1 and 2)
- To show that the MB-102 transdermal fluorescence measured GFR using the ORFM Brilliance device aligns with the measured MB-102 plasma GFR (Group 3)
- To evaluate the safety and effectiveness of the ORFM investigational medical device prototypes QuantumLeap, Radiance and Brilliance for the non-invasive transdermal fluorescent detection of MB-102 on subjects with a range of skin color types
- To determine the optimum dose of MB-102 for non-invasive measurement

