All derived results for pharmacokinetic parameters will be summarized numerically by agent. For categorical variables, the frequency of subjects will be provided along with the percentage based on the number of subjects with available data. Summaries will be based on observed data (i.e., no missing data will be imputed) and will include all dosed subjects completing all aspects of the study.

An analysis of variance of estimated GFR will be performed taking into account the factors subjects, treatments (MB-102 and iohexol), CKD stage and skin color type.

[figure not shown]
All plasma and urine concentrations will be provided in listings by subject and time point. Any blood measurements obtained outside of the defined windows around the scheduled time point will be identified as protocol deviations. Additionally, pharmacokinetic parameters will be provided in listings sorted by subject.

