# 9.1.3.1 Analysis of ORFM Fluorescence Data (tGFR) vs PK Data for GFR Determination

A correlation between the fluorescence intensity and tracer concentration at each time point in the renal excretion phase will be performed to establish that the transdermal fluorescence pharmacokinetics matches the plasma pharmacokinetics. Summaries of the data will be performed to evaluate the effects of skin color and CKD stage on the correlation.

[figure not shown]
Data from a Pilot 1B study shows that plotting plasma concentration versus fluorescence intensity at the same time points in the renal excretion phase yields a tight correlation (**Figure 2**). The data shown in this correlation are from healthy subjects with normal renal function (measured by eGFR) who received a 4 µmol/kg dose.

[figure not shown]
Figure 2 Correlation between Plasma Pharmacokinetics and Fluorescence Pharmacokinetics in Pilot 1B, Subject 12

In the Pilot 2 Group 1 clinical study, this type of correlation was observed across subjects with GFR values over the entire range. Examples are shown below (**Figure 3**):

Figure 3 Transdermal fluorescence correlates with plasma Pharmacokinetics over a range of GFR

From the Pilot 2 Group 1 plasma measured GFR from MB-102 and the fluorescence decay constant from all subjects, a very preliminary correlation plot has been constructed (**Figure 4**), similar to the graph as done in Rabito et. al. 2010 (**Figure 5**).

Figure 4 Correlation between Plasma GFR and Trans-cutaneous Fluorescence Clearance Rate (with Volume of Distribution (VD) correction of GFR)

[figure not shown]
[figure not shown]

Figure 5 Correlation between GFR measured as renal clearance of 125I-iothalamate and the rate of clearance of 99mDTPA

Further analysis of the data will be done to determine the optimum data conversion using volume of distribution, body surface area, and possibly other factors.

For Pilot 2 Group 2 subjects, this type of graph will be used to convert the measured fluorescence time constant "fluorescence GFR" and then compare that value with the MB-102 plasma measured GFR from the same subjects. The database will also be updated with this new data to make the algorithm more robust for the pivotal studies to follow.

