### 13 Post-Dose Procedures by Group and Cohort

### 13.1 Group 1 (Cohorts 1 and 2) and Group 2 (Cohorts 3 and 4 subset)

- Single dose
- Cohort 1 and 3: healthy to stage 2 CKD: enrolled 50 subjects
- Cohort 2 and 4: compromised renal function: enrolled 60 subjects
- 12 hour follow-up
- Iohexol administration
- Urine collection

Post-dose study procedures will be performed at the following timepoints:

- PK draw (6 mL blood) in K2 EDTA tube at 5 minutes (±1 minute)
- Vital sign collection at 6 minutes (±1 minute)
- PK draw (6 mL blood) in K2 EDTA tube at 10 minutes (±2 minute)
- Vital sign collection at 11 minutes (±1 minute)
- PK draw (6 mL blood) in K2 EDTA tube at 15 minutes (±2 minute)
- Vital sign collection at 16 minutes (±1 minute)
- PK draw (6 mL blood) in K2 EDTA tube at 30 minutes (±5 minutes)
- Vital sign collection at 35 minutes (±5 minutes)
- An ECG will be conducted at 55 minutes (±5 minutes)
- PK draw (6 mL blood) in K2 EDTA tube at 60 minutes (±5 minutes)
- Vital sign collection at 65 minutes (±5 minutes)
- PK draw (6 mL blood) in K2 EDTA tube at 90 minutes (±5 minutes)
- Vital sign collection at 95 minutes (±5 minutes)
- An ECG will be conducted at 115 minutes (±5 minutes)
- PK draw (6 mL blood) in K2 EDTA tube at 120 minutes (±5 minutes)
- Vital sign collection at 125 minutes (±5 minutes)
- PK draw (6 mL blood) in  $K_2$  EDTA tube at 180 minutes ( $\pm 5$  minutes)

- Vital sign collection at 185 minutes (±5 minutes)
- An ECG will be conducted at 235 minutes (±5 minutes)
- PK draw (6 mL blood) in  $K_2$  EDTA tube at 240 minutes ( $\pm 5$  minutes)
- Vital sign collection at 245 minutes (±5 minutes)
- PK draw (6 mL blood) in  $K_2$  EDTA tube at 300 minutes ( $\pm 5$  minutes)
- Vital sign collection at 305 minutes (±5 minutes)
- PK draw (6 mL blood) in K2 EDTA tube at 360 minutes (±10 minutes)
- Vital sign collection at 365 minutes (±5 minutes)
- PK draw (6 mL blood) in K2 EDTA tube at 480 minutes (±10 minutes)
- Vital sign collection at 485 minutes (±5 minutes)
- PK draw (6 mL blood) in  $K_2$  EDTA tube at 600 minutes ( $\pm 10$  minutes)
- Vital sign collection at 605 minutes (±5 minutes)
- PK draw (6 mL blood) in  $K_2$  EDTA tube at 720 minutes ( $\pm 10$  minutes)
- Clinical laboratory (safety labs) draw at 720 minutes (±10 minutes) (chemistry, hematology, lipids, and coagulation). The venous catheter may be removed.

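### Run with the factors it lists, the GFR ANOVA gives one overall MB-102 versus iohexol difference, while the endpoint concerns that comparison in normal and in impaired renal function

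*Combined protocol and SAP*

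**What the plan says.** The primary endpoint for Groups 1 and 2 (Synopsis, Primary Endpoint) is MB-102 plasma PK, "compared to the pharmacokinetics of iohexol in subjects with normal and impaired renal function and a range of skin color types". Section 4 repeats the renal-function part as an objective for the same groups. The Synopsis (Treatment) has every Group 1 and 2 subject receive one dose of each agent, so each subject contributes two GFR values.

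Section 9.1.3 gives the comparison one sentence, on an ANOVA: "variance of estimated GFR will be performed taking into account the factors subjects, treatments (MB-102 and iohexol), CKD stage and skin color type". Subject is among the named factors. The sentence does not mention interactions, raw or log GFR, or whether subject is fixed or random. The same section says "All derived results for pharmacokinetic parameters will be summarized numerically by agent", with no split by CKD stage.

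Section 9.1.3.1 does consider CKD stage and skin color as modifiers: "Summaries of the data will be performed to evaluate the effects of skin color and CKD stage on the correlation". That correlation is between transdermal fluorescence and plasma MB-102, not between MB-102 and iohexol.

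**The concern.** Whether MB-102 agrees with iohexol may depend on renal function, and the endpoint names both ends of the range. The appended iohexol package insert (Section II, Clinical Pharmacology) says that excretion through the gallbladder and small intestine may increase in severe renal impairment. Section 5.7 describes MB-102 as filtered by the kidney and not expected to be metabolised by the liver or other organs. This makes a difference in advanced CKD plausible; it does not show that one occurs.

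Listing CKD stage as a factor may look as if it covers the question, but a main effect of CKD stage does not. It describes how GFR itself varies with stage, not how the difference between the two agents varies. If only the listed factors are fitted, a disagreement limited to impaired subjects is averaged with the agreement in normal subjects, and the output cannot show where it arises.

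**Working it through.** The plan gives no sample size calculation, alpha, power or margin for this analysis, so there is no figure of its own to reproduce.

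**Inputs from the documents.** Section 13.1 gives 50 subjects with normal to stage 2 function ("Cohort 1 and 3: healthy to stage 2 CKD: enrolled 50 subjects") and 60 with compromised function. Section 13.2 adds 10 in the extended-PK subgroup. Impaired total: 60 + 10 = 70. Overall: 50 + 70 = 120 subjects, two agents each, 240 GFR values.

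**Assumed inputs.** Effect sizes, within-subject CVs (5% to 15% per agent), GFR ranges and the split by CKD stage are not in the documents.

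**1. What the listed factors can estimate.** Rank of the design matrix:

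| Terms | Rank |
|---|---|
| subject + agent | 121 |
| + CKD stage + skin type main effects | 121 |
| + agent x CKD, two CKD levels | 122 |
| + agent x CKD, five CKD levels | 125 |

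The CKD and skin main effects add nothing once subject is in the model as fixed. The agent coefficient is then the mean paired difference over 120 subjects, on 240 − 121 = 119 residual degrees of freedom. With a random subject effect, CKD and skin effects become estimable, but only on GFR averaged over the two agents. The agent estimate does not change: in simulated paired data it was −0.464 under the mixed model and −0.464 as the mean paired difference.

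**2. Averaging over strata (assumed differences, mL/min).**
- +4.75 normal, +1.75 impaired: (50 × 4.75 + 70 × 1.75)/120 = 360/120 = 3.00.
- +5.00 normal, −3.57 impaired: (50 × 5.00 − 70 × 3.57)/120 ≈ 0.00.

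Adding agent x CKD group recovers the two separate values in each case.

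**3. Dilution on the log scale.** If a ratio d applies in m of the 120 subjects and 1 elsewhere, the overall geometric mean ratio is d^(m/120). With d = 1.15:
- all 70 impaired: 1.15^(70/120) = 1.085
- 48 subjects (assumed number in stages 4–5): 1.15^(48/120) = 1.057
- 24 subjects (assumed): 1.15^(24/120) = 1.028

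**4. Dilution on the raw scale.** Simulation with GFR uniform on 60–120 (n = 50), 30–59 and 8–30 (24 or 48 of the 70 impaired), and a 15% over-read in all 70. The overall difference is about 2.4–3.2 mL/min, against about 4.1–5.4 mL/min within the impaired group.

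**5. Correlation.** In the same simulation, the correlation between the two GFRs is 0.910–0.992 without the over-read and 0.898–0.989 with it.

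**6. Why the scale matters.** At assumed GFRs of about 95 (normal) and 35 (impaired), a constant 5% bias is about +4.7 and +1.7 mL/min, but a ratio of 1.05 in both groups. A constant +3 mL/min is a ratio of about 1.03 in normal and 1.10 in impaired. Raw and log analyses can therefore disagree on whether the agents differ by stratum.

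**7. Precision of a stratified analysis.** Half-width of the 95% CI on a ratio = exp(t(0.975, m−1) × √2 × s/√m) − 1, with s = √ln(1 + CV²):

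| Stratum | CV 5% | CV 15% |
|---|---|---|
| overall, 120 | 1.3% | 3.9% |
| impaired, 70 | 1.7% | 5.2% |
| normal, 50 | 2.0% | 6.2% |
| a stage stratum of 24 (assumed) | 3.0% | 9.3% |

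The impaired-to-normal ratio of ratios uses √2 × s × √(1/50 + 1/70) on 118 degrees of freedom: 2.6% to 8.0%.

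**The case against.** The sentence names factors, not model terms, and does not say main effects only. Since CKD stage and skin type add nothing to a paired comparison unless they interact with agent, listing them may mean that interactions were intended. A figure after the sentence is not visible. Section 9.1.4 (Clinical Laboratory Assessments) and section 9.1.8 point to a Statistical Analysis Plan for other matters, and model details often sit there. This stands: the defect is an incompletely specified model. A reader might infer that the plan rules out interactions or contradicts its endpoint; the text supports neither.

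A reader might also infer that the model ignores the pairing. It does not, because subject is a named factor. Only its fixed or random status is unstated, and that does not change the agent estimate in complete paired data.

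The endpoint wording could be read as describing the population studied rather than asking for estimates by stratum. That reading is possible, but a pooled figure is still a poor answer where the endpoint and objective both single out normal and impaired function. Listings of PK parameters by subject would let someone assemble the comparison by hand, but no visible section plans it.

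The magnitudes are hypothetical, and a 15% over-read would not vanish: 1.085 and 1.057 both lie further from 1 than the widest overall half-width of 3.9%. This also stands. The bias would be diluted and unlocalised rather than hidden, except perhaps in the 1.028 case at the higher assumed CVs.

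Finally, section 3.3 already reports "A high correlation between the MB-102 and iohexol plasma derived GFR values". That does not settle the matter, since correlation hardly moves under the assumed bias.

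**Conclusion.** The point holds, with moderate confidence. As listed, the ANOVA yields one pooled MB-102 versus iohexol difference weighted 50:70, PK parameters are summarised by agent only, and no visible section compares the agents by renal function. Under the assumed 15% over-read in the 70 impaired subjects, the overall ratio would be about 1.085, with nothing in the output to locate the difference.

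The weighting and rank results rest on the documented group sizes, complete pairs and the model being fitted as listed. The size of any dilution rests on assumed effects. A reader might infer that MB-102 and iohexol actually diverge in CKD; nothing in the documents shows this.

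The consequence is limited: section 5.5.1 calls the study hypothesis-generating, no decision rule rests on this analysis, and the paired data are retained. The gap should be fixed because it affects a primary endpoint and the repair is cheap. An agent-by-skin-type term is not essential, since both GFRs come from plasma and skin color has little reason to alter their ratio.

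**What to change.** State the scale and the status of subject. Model each subject's log(GFR MB-102 / GFR iohexol) on CKD group. Equivalently, fit log GFR with random subject and fixed agent, CKD stage and agent x CKD stage. Report geometric mean ratios with 95% confidence intervals overall and by CKD group, labelled exploratory. Summarise PK parameters by agent within CKD group. A breakdown by skin type is optional.

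The cost is plan wording and some reprogramming. The Synopsis reports Groups 1 and 2 complete, so no new data are needed, but the added terms cannot be presented as prespecified. Stratum intervals are wider than the overall one: about 1.3 times for the 70 impaired (1.7/1.3 or 5.2/3.9), and more for single CKD stages.

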# 9.1.3.1 Analysis of ORFM Fluorescence Data (tGFR) vs PK Data for GFR Determination

A correlation between the fluorescence intensity and tracer concentration at each time point in the renal excretion phase will be performed to establish that the transdermal fluorescence pharmacokinetics matches the plasma pharmacokinetics. Summaries of the data will be performed to evaluate the effects of skin color and CKD stage on the correlation.

[figure not shown]
Data from a Pilot 1B study shows that plotting plasma concentration versus fluorescence intensity at the same time points in the renal excretion phase yields a tight correlation (**Figure 2**). The data shown in this correlation are from healthy subjects with normal renal function (measured by eGFR) who received a 4 µmol/kg dose.

[figure not shown]
Figure 2 Correlation between Plasma Pharmacokinetics and Fluorescence Pharmacokinetics in Pilot 1B, Subject 12

In the Pilot 2 Group 1 clinical study, this type of correlation was observed across subjects with GFR values over the entire range. Examples are shown below (**Figure 3**):

Figure 3 Transdermal fluorescence correlates with plasma Pharmacokinetics over a range of GFR

From the Pilot 2 Group 1 plasma measured GFR from MB-102 and the fluorescence decay constant from all subjects, a very preliminary correlation plot has been constructed (**Figure 4**), similar to the graph as done in Rabito et. al. 2010 (**Figure 5**).

Figure 4 Correlation between Plasma GFR and Trans-cutaneous Fluorescence Clearance Rate (with Volume of Distribution (VD) correction of GFR)

[figure not shown]
[figure not shown]

Figure 5 Correlation between GFR measured as renal clearance of 125I-iothalamate and the rate of clearance of 99mDTPA

Further analysis of the data will be done to determine the optimum data conversion using volume of distribution, body surface area, and possibly other factors.

For Pilot 2 Group 2 subjects, this type of graph will be used to convert the measured fluorescence time constant "fluorescence GFR" and then compare that value with the MB-102 plasma measured GFR from the same subjects. The database will also be updated with this new data to make the algorithm more robust for the pivotal studies to follow.

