# 6.5 Iohexol Dosing (Groups 1 and 2 only)

- 5 mL of iohexol will be administered as a bolus via IV over approximately 30 seconds
- 10 mL saline flush will be administered via IV over approximately 30 seconds

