# **Clinical Laboratory Assessments**

Clinical laboratory tests include clinical chemistry, hematology, urinalysis and coagulation parameters. Each parameter will be summarized using the most appropriate descriptive statistics. Details will be specified in the Statistical Analysis Plan (SAP). Also, individual subject results will be assessed against an appropriate reference range if available. The manifestation of any clinically significant abnormality that develops during the study will be reported as an AE.

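### Group 3's primary endpoint is agreement of device GFR with plasma GFR, but section 9.1.3.1 states a GFR-to-GFR comparison for Group 2 only and judges skin-color and CKD-stage effects on a correlation that barely responds to GFR error

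*Combined protocol and SAP*

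**What the plan says.** The synopsis gives as the Group 3 primary endpoint to show that "MB-102 transdermal fluorescence measured GFR using the ORFM Brilliance device matches the measured MB-102 plasma GFR". A secondary endpoint is device effectiveness, assessed "through the comparison of fluorescent measurements versus MB-102 across the three groups of subjects". Section 5.2.2 adds that the fixed dose in part of SeVG and in Cohorts 7 and 8 is tested partly to see whether the device GFR (tGFR) remains accurate.

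Three analyses in section 9 bear on this:

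- **Section 9.1.3.1, no group named:** "A correlation between the fluorescence intensity and tracer concentration at each time point in the renal excretion phase will be performed". The stated purpose is to establish that the fluorescence and plasma pharmacokinetics match. Then: "Summaries of the data will be performed to evaluate the effects of skin color and CKD stage on the correlation".
- **Section 9.1.3.1, Group 2:** "For Pilot 2 Group 2 subjects, this type of graph will be used to convert the measured fluorescence time constant" into a GFR, which is then compared with the same subjects' plasma GFR. No statistic is given.
- **Section 9.1.3:** an analysis of variance of GFR with "the factors subjects, treatments (MB-102 and iohexol), CKD stage and skin color type". Section 6.5 restricts iohexol to Groups 1 and 2.

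Section 9.1.3.1 also plots Group 1 plasma GFR against the fluorescence decay constant. That plot is a calibration, not a comparison of two GFR values.

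**The concern.** A reader who follows section 9 literally for Group 3 reaches the intensity-concentration correlation and nothing at the level of GFR. The analysis of variance needs iohexol, which Group 3 does not receive. The Group 2 method could carry over, but the text does not say so and gives no metric for either group.

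This is more than missing detail, because the text does state how skin-color and CKD-stage effects are to be judged: by what happens to the correlation. Performance across skin types is a study objective (section 4). If the device read low in one skin group and high in the other, summaries of r could look alike in both. The data are to be summarized for pivotal regulatory discussions (section 9.1.5), where the size of the GFR error is what a reader will want.

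**Working it through.** The plan gives no figure to reproduce: there is no alpha, margin, sample-size calculation or SD for the device error. The check asks how far r moves when device GFR is wrong.

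**Why r is the wrong scale.** In the renal excretion phase let plasma concentration be C = exp(-kt) and fluorescence F = exp(-ckt), where c = 1 is a correct decay rate. With volume of distribution held fixed, GFR is proportional to the rate, so c is the ratio of device GFR to plasma GFR. Then log F = c × log C. The GFR error is the slope c. The correlation discards the slope: on the log scale r is exactly 1 for any positive c.

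**Within a subject, natural scale.** Inputs:

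- Sampling times 120, 180, 240, 300, 360, 480, 600 and 720 min, from the 12-hour schedule in section 5.3.2. Taking these as the renal excretion phase is an assumption.
- Half-life about 2 h with normal kidneys (section 3.1), so k = ln 2 / 120 = 0.00578 per min.
- Independent log-normal noise of 5% on both signals (assumed).
- Median Pearson r over 60,000 draws.

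| Rate error | c | r, no noise | r, 5% noise |
|---|---|---|---|
| 30% too slow | 0.70 | 0.993 | 0.990 |
| 15% too slow | 0.85 | 0.998 | 0.996 |
| none | 1.00 | 1.000 | 0.997 |
| 15% too fast | 1.15 | 0.999 | 0.996 |
| 30% too fast | 1.30 | 0.995 | 0.993 |

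One skin group 15% too slow and the other 15% too fast gives 0.996 in both, against 0.997 for a correct device. At an assumed 8 h half-life on the same 12-hour schedule the pair is 0.971 and 0.978, against about 0.975 when correct, so the group reading too fast scores above a correct device. Cohort 8 is sampled to 24 or 48 h, so the 8 h case applies to cohorts on the 12-hour schedule.

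**Across subjects at each time point.** The wording also allows this reading. Assume 141 subjects, half in each skin group, GFR uniform on 15 to 120, a 2 h half-life at GFR 100, 5% random rate error and 10% between-subject variation in signal per unit concentration. Mean r over the eight times:

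- no bias: 0.964
- GFR 20% too low in one skin group: 0.939, with only 56% of all subjects within 15% of plasma GFR
- signal cut to 0.3 in one skin group, no GFR error: 0.632

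On this reading r responds far more to signal loss, which need not affect GFR, than to a real GFR error.

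**What a paired analysis would deliver.** For d = log(tGFR / plasma GFR), the 95% CI half-width on mean bias is t × SD / √n. The documents give no SD; take 0.10 to 0.20.

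- n = 48 (the synopsis maximum for Cohorts 7 and 8): 2.012 × 0.10 / √48 = 0.029, and 0.058 at SD 0.20, so about 3% to 6%.
- n = 32 (the 16 + 16 in the section 5.5.2 headings): 2.040 × 0.10 / √32 = 0.036, and 0.072 at SD 0.20.
- Skin-group difference, 24 against 24: 2.013 × 0.10 × √(2/24) = 0.058, and 0.116 at SD 0.20.

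**The case against.** The strongest reply is that this is under-specification and not a wrong choice. The correlation is offered to show that the pharmacokinetics match, which suits the secondary endpoint; nothing presents it as the test of the Group 3 primary endpoint. A reader might infer that it is that test, or that no Group 3 GFR comparison is planned. The documents support neither. The endpoint itself, the section 5.2.2 remark on tGFR accuracy and the title of section 9.1.3.1 all show that a comparison is intended, and the Group 2 conversion method would carry over. This stands, and it limits the point to what section 9.1.3.1 states.

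The protocol also refers to a separate Statistical Analysis Plan, under Clinical Laboratory Assessments and in section 9.1.8, which was not supplied. Those references concern laboratory summaries and imputation, but a Group 3 analysis could still be there. That stands as a limit too.

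A skin-stratified plot, or a slope of log fluorescence on log concentration, could reveal a rate difference. Neither is stated; the text says only that effects on the correlation will be summarized.

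Finally, the study is hypothesis generating (section 5.5.1) with no formal sample size, and no value of r triggers a decision. That lowers the stakes. It does not make r an estimate of GFR error, and estimation is what a pilot is for.

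**Conclusion.** The point holds for the supplied text and should be fixed. The Group 3 primary endpoint has no stated estimate or metric, and the stated way of judging skin-color and CKD-stage effects on the device is insensitive to the error that matters. In the worked case, a 30% error in decay rate moves r from 0.997 to about 0.99, and opposite 15% errors by skin group leave r at 0.996 in both.

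These figures rest on an assumed 5% noise, a single-exponential decay, fixed volume of distribution and chosen error sizes; other values would change the decimals. The slope argument depends on the decay model but not on the noise level or the size of the error.

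A reader might go further and attach a probability that the plan would miss a skin-type bias. The documents do not support one: they plan summaries, not a test of r between skin groups, and give neither the device-error SD nor the variation in signal per unit concentration. Nor does anything here show that the device is biased.

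**What to change.** In section 9.1.3.1, name Group 3 and state a paired per-subject comparison of tGFR with MB-102 plasma GFR, for example the log ratio or percent difference. Report mean bias with its 95% CI and limits of agreement, overall and by skin group and CKD stage. Judge skin-color and CKD-stage effects on that difference. Keep the intensity-concentration correlation as description of pharmacokinetic matching, and say whether it is computed within or across subjects.

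Report the cohorts used to optimize the algorithm or sensor (Cohorts 5 and 6, SOG, and any Cohort 7 or 8 set used for retuning) separately from the test cohorts, because agreement in data used for tuning tends to look better than it is.

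The cost is wording and a few tables, with no new subjects or samples. The headline will probably look less favorable than a correlation near 1. Precision will be moderate: about 3% to 6% either side of the mean bias at n = 48 under the assumed SDs, and wider by skin group or CKD stage. If the separate SAP already contains this analysis, a cross-reference from section 9.1.3.1 is enough.
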